4.3.2.1.1 Dose Adjustments of Mircera

Dose adjustments may be performed during the entire study. The dose of Mircera should be adjusted to maintain the individual patient's Hb within a target range of ± 1 g/dL of his or her baseline Hb and between 10.0–12.0 g/dL. Baseline Hb is calculated as the mean of Hb values obtained at Visit 1 (Week –3) and Visit 2 (Week –1).

Dose adjustments should be performed at the scheduled dosing days and should be based on the Hb value measured on that day. They should not be performed more often than once every 4 weeks.

Dose adjustment rules for Mircera in response to Hb changes, including those required for safety reasons, are summarized in [Table 3](#).

Table 3 Mircera Dose Adjustments

Hemoglobin Assessment	Compared with the Previous Mircera Dose
Hb decreases by more than 1.0 g/dL compared with baseline Hb.	Increase dose by approximately 25% (or closest higher PFS strength).
Hb is less than 10 g/dL and greater than or equal to 9 g/dL (Hb < 10.0 and ≥ 9.0 g/dL).	Increase dose by approximately 25% (or closest higher PFS strength).
Hb is less than 9 g/dL (Hb < 9.0 g/dL).	Increase dose by approximately 50% (or closest to 50% increase PFS strength).
Hb increases by more than 1.0 g/dL compared with the baseline Hb.	Decrease dose by approximately 25% (or closest lower PFS strength).
Hb is increasing and is approaching 12 g/dL or Hb is greater than or equal to 12 g/dL (Hb ≥ 12 g/dL).	Decrease dose by approximately 25% (or closest lower PFS strength).
If Hb exceeds 12 g/dL and continues to increase following a dose reduction.	Stop doses until Hb is less than 12.0 g/dL. Resume dose at approximately 25% below previous dose (or closest lower PFS strength) at next scheduled dosing day.

Hb = hemoglobin; PFS = *prefilled syringe*..

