4.1.2 Exclusion Criteria

Patients who meet any of the following criteria will be excluded from study entry:

- Overt gastrointestinal bleeding within 8 weeks before screening or during the screening period
- RBC transfusions within 8 weeks before screening or during the screening period
- Hemoglobinopathies (e.g., homozygous sickle-cell disease, thalassemia of all types)
- Hemolytic anemia
- Active malignant disease
- PD subjects with an episode of peritonitis within the past 30 days prior to screening and/or during the screening period
- Uncontrolled or symptomatic inflammatory disease (e.g., systemic lupus erythematosus)
- Uncontrolled hypertension as assessed by the investigator (for standard blood pressure reference tables, see [Appendix 6](#))
- Epileptic seizures within 3 months prior to screening and during the screening period
- Administration of any investigational drug within 4 weeks prior to screening or planned during the study
- *Kidney transplant with use of immunosuppressive therapies known to exacerbate anemia (see Section 4.4.5)*
- Severe hyperparathyroidism (intact parathyroid hormone [PTH] ≥ 1000 pg/mL or whole PTH ≥ 500 pg/mL) or biopsy-proven bone marrow fibrosis
- Known hypersensitivity to recombinant human EPO, polyethylene glycol, or any constituent of the study drug formulation
- Anti-EPO antibody (AEAB)-mediated pure red cell aplasia (PRCA) or history of AEAB-mediated PRCA or positive AEAB test result in the absence of PRCA
- High likelihood of early withdrawal or interruption of the study (e.g., planned living donor kidney transplant within 5 months of study start)
- Planned elective surgery during the entire study period
- Females who are pregnant or breastfeeding or who intend to become pregnant during the study or within 90 days after the final dose of Mircera

Note: Patients of childbearing potential must have a negative serum pregnancy test result within 21 days prior to initiation of study drug.

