5.3.5.10 Loss of Effect

Hb values will be monitored regularly throughout the study, and dose adjustments to achieve target Hb will be made according to protocol guidance (see Section [4.3.2.1.1](#)).

Loss of effect is defined as follows: a decline in Hb of at least 2.8 g/dL in a 4-week period without transfusion or requirement for transfusion of 1 blood unit or more per week for a minimum of 2 consecutive weeks in the absence of overt bleeding or blood loss, under uninterrupted treatment with study drug and with dose changes according to protocol guidance (Eckardt and Casadevall 2003). If loss of effect is suspected, the cause should be actively sought. Possible causes include the following: iron deficiency, infection, inflammation, occult blood loss, hyperparathyroidism, myelofibrosis, and malignancy. If a cause for loss of effect is not found, a hematologist should be consulted (possible bone marrow examination), and an unscheduled blood sample should be obtained for a reticulocyte count and an anti-EPO and anti-Mircera antibody determination. An additional blood sample should also be stored for an anti-PEG antibody determination after the assay has been developed.

If a diagnosis of PRCA is not confirmed, the patient should be maintained on the IMP, and other possible causes of loss of effect should be investigated.

If a diagnosis of PRCA is confirmed, treatment with the IMP should be stopped. The patient should not receive another epoetin, and causes of PRCA should be investigated. Reticulocyte counts and anti-EPO, anti-Mircera, and anti-PEG antibody testing will be performed every 8 weeks until the end of the study (see [Appendix 4](#) for further, detailed guidance).

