6.4 EFFICACY ANALYSES

All efficacy variables (original values and change from baseline) over time will be presented in summary tables and graphically. The estimates will be summarized descriptively using means, standard deviations, and percentiles.

The analysis population for the primary and secondary efficacy analyses will be the ITT population consisting of all enrolled patients.

An additional analysis will be performed based on the per-protocol population, which will be precisely defined in the statistical analysis plan, before database closure, as the subset of the ITT population without major protocol deviations.

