###### **4.1.2 Per Protocol Population**

The Per-Protocol (PP) population is defined as all patients included in the safety population and who have no major protocol deviations as defined below.

1. Patients with less than 3 Hb values during the evaluation period.
2. Patients who miss any application of study medication at week 13 or week 17.
3. Patients with an overdose of Mircera at week 17 captured as a protocol deviation
4. Patient with wrong Mircera starting dose
5. Patients who do not fulfill the inclusion criteria for:
  - hemoglobin
  - iron levels
  - stable dose and dosing interval of SC treatment with epoetin alfa, epoetin beta or biosimilars, or darbepoetin alfa
6. Patients who fulfill any of the exclusion criteria:
  - Hemolytic anemia
  - Use of prohibited therapy

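### The per-protocol list in SAP 4.1.2 leaves out several entry breaches that the protocol itself ties to lost ESA response

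*Protocol*

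**What the plan says.** Protocol 6.4 puts the primary and secondary efficacy analyses on ITT and announces an additional per-protocol analysis. It describes that set as "the subset of the ITT population without major protocol deviations" and leaves the exact definition to the SAP.

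SAP 4.1.2 defines the set as "all patients included in the safety population and who have no major protocol deviations as defined below" and gives six numbered items:

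- Item 1 concerns too few Hb values in the evaluation period.
- Items 2 to 4 concern dosing: a missed dose at Week 13 or 17, a Week 17 overdose captured as a deviation, and "Patient with wrong Mircera starting dose".
- Item 5 concerns inclusion criteria, limited to Hb, iron, and stable ESA dose and interval.
- Item 6 opens with "Patients who fulfill any of the exclusion criteria" and then names two things: hemolytic anemia and use of prohibited therapy.

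No item refers to Table 3, where Protocol 4.3.2.1.1 sets out the "Dose adjustment rules for Mircera in response to Hb changes, including those required for safety reasons".

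Protocol 5.3.5.10, on loss of effect, says: "Possible causes include the following: iron deficiency, infection, inflammation, occult blood loss, hyperparathyroidism, myelofibrosis, and malignancy". Protocol Appendix 4, section 3.1, gives a longer list that adds hemoglobinopathies and inadequate dialysis. Protocol 5.1.1.2 and Appendix 4, section 4, describe anti-EPO antibodies as a cause of ESA resistance.

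**The concern.** Several conditions that bar entry under Protocol 4.1.1 and 4.1.2 are conditions that the protocol elsewhere gives as reasons for an ESA to stop working. A patient enrolled with one of them has breached entry in a way that can move Hb, yet no item in SAP 4.1.2 removes that patient.

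The per-protocol analysis is the only pre-announced re-estimate of the mean Hb change without major deviators. If it keeps these patients, it could agree with ITT partly because both sets contain the same breaches. What is at stake is the value of that supporting analysis. The primary estimate does not depend on it.

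**Working it through.** **1. Entry criteria set against the per-protocol list.**

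| Entry criterion (Protocol 4.1.1, 4.1.2) | Where the protocol ties it to lost response | Removed by SAP 4.1.2? |
|---|---|---|
| Hemoglobinopathy | Appendix 4, 3.1 | No |
| Overt GI bleeding | 5.3.5.10 and Appendix 4, 3.1 name occult and chronic blood loss; the loss-of-effect definition treats overt bleeding as a separate explanation of an Hb fall | No |
| Active malignancy | 5.3.5.10; Appendix 4, 3.1 | No |
| Inflammatory disease | 5.3.5.10; Appendix 4, 3.1 | No |
| Peritonitis | 5.3.5.10 (as infection) | No |
| Severe hyperparathyroidism or marrow fibrosis | 5.3.5.10; Appendix 4, 3.1 | No |
| Anti-EPO antibody or antibody-mediated PRCA | 5.1.1.2; Appendix 4, section 4 | No |
| PD adequacy; HD adequacy | Appendix 4, 3.1 | No |
| Hb, iron, ESA dose, ESA interval | Iron: 5.3.5.10 | Yes, item 5 |
| Hemolytic anemia | Appendix 4, 3.1 | Yes, item 6 |
| Pre-study RBC transfusion; transplant with immunosuppression | Immunosuppressants: Appendix 4, 3.1 | Transfusion yes, transplant largely, through prohibited therapy (Protocol 4.4.5) |

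Of the seven causes named in Protocol 5.3.5.10, only iron deficiency maps to a per-protocol item.

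**2. Count.** A broad count gives 18 entry criteria that could bear on Hb. It adds the eGFR/dialysis-duration criterion (not covered) and the investigational-drug criterion (covered) to the table. Eight are covered and 10 are not (10/18 = 56%). Without those two, 7 are covered and 9 are not (9/16 = 56%).

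**3. When a breach can surface.** A positive anti-EPO antibody is an exclusion (Protocol 4.1.2). Appendix 1 schedules no antibody test at screening. The first sample is drawn pre-dose at Week 1 and goes to an outside laboratory (4.5.6.1), so a positive result can become known after dosing has begun.

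**4. The plan's own figure.** Protocol 6.1 and SAP 2.3 state about 90% power that the 90% CI lies within ±1 g/dL, with n = 26, SD 1.5 and true change 0.

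- t-based power, integrating over the sampling distribution of the SD, is 0.903. The figure reproduces.
- The normal approximation is 2Φ(√26/1.5 − 1.645) − 1 = 0.921.
- Expected CI half-width: 1.708 × 1.5/√26 = 0.502 g/dL.

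**5. Size of the effect of retained breaches.** The documents give no breach rate and no Hb effect, so these inputs are assumed.

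- One patient at −3 g/dL and 25 others with mean 0, SD 1. Mean = −3/26 = −0.115. Variance = (24 × 1² + 9 − 26 × 0.115²)/25 = 1.306, so SD = 1.143. Lower 90% limit = −0.115 − 1.708 × 1.143/√26 = −0.498. With mean 0 and SD 1 throughout it is −1.708/√26 = −0.335.
- k patients each displaced downward by d g/dL move the mean by k × d/26. With the overall SD held at 1.5 (half-width 0.502):

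| k | d | Shift in mean | Lower 90% limit |
|---|---|---|---|
| 2 | 1.0 | −0.077 | −0.58 |
| 4 | 1.5 | −0.231 | −0.73 |
| 6 | 2.0 | −0.462 | −0.96 |

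- To reach −1 the displacements must total 26 × (1 − 0.502) = 12.9 g/dL. At 3 g/dL each, four patients (12) are not enough and five (15) are.

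**6. Cost of removing patients.** At SD 1.5, going from n = 26 to 24, 22 or 20 widens the half-width from 0.502 to 0.525, 0.550 or 0.580. Power falls from 0.90 to 0.87, 0.83 or 0.78.

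**The case against.** The strongest reply is that a short list is a legitimate choice. Protocol 6.4 delegates the definition to the SAP. Eligibility must be confirmed before enrollment (4.5.1) and waivers are not allowed (9.2), so breaches should be few. Primary and secondary analyses are on ITT, and SAP 4.3 names no per-protocol output. SAP 4.2 already lists major deviations and evaluates their effect on interpretation. All of this stands and limits the weight of the point. It does not close the gap: listing deviations does not re-estimate the mean and CI without them, and pre-enrollment checks cannot catch an antibody result that arrives after the first dose.

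Item 6 might instead be read as covering every exclusion criterion, with two examples. Item 5 has the same form and is clearly restrictive, and the definition points to deviations listed below it, so two items only is the natural reading. The SAP should say so either way.

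A reader might infer that the list lets through most Hb-relevant breaches, or those most likely to move Hb. The documents do not support that. The majority is bare and depends on what is counted, and the most direct breaches are removed: Hb, iron, ESA stability, hemolysis and, through prohibited therapy, pre-study transfusion and immunosuppressants.

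A reader might also infer that dosing against Table 3 at Weeks 5 to 13 should remove a patient. It is true that no item covers it. If 5%, 10% or 20% of decisions departed from Table 3 (assumed, independent across three visits), 1 − (1 − q)³ gives 14%, 27% or 49% of patients. The documents supply neither a rate nor a link to Hb, so this does not size a bias. Neither document says that the set is meant to isolate patients dosed to rule.

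The exclusion would also do harm. Protocol 4.3.2.1.1 says: "Dose adjustments should be performed at the scheduled dosing days and should be based on the Hb value measured on that day". An omitted adjustment can therefore arise only once on-treatment Hb has left range, and dropping such patients selects on the outcome. It could pull the mean toward zero and shrink the SD, favoring the SAP 4.3.1 verdict that the conversion factor is appropriate.

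Nor can adherence yet be coded cleanly. With baseline Hb of 10 to 12, any Hb below 9 meets two Table 3 rows with different steps. The no-change instruction after transfusion for acute blood loss (4.3.2.1.2) can conflict with the low-Hb rows. The stop/resume row depends on earlier Hb and doses. These passages must be reconciled first; no view is taken here on which rule is right.

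**Conclusion.** The point holds in a limited form. SAP 4.1.2 omits seven exclusion criteria and the two dialysis-adequacy criteria that the protocol ties, directly or through a close equivalent, to lost ESA response. Patients who breach them stay in a set that Protocol 6.4 describes as free of major deviations.

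The effect is confined to the additional per-protocol analysis; the ITT primary result is unaffected. On the assumed figures, one marked non-responder leaves the interval well inside ±1 g/dL, and about five at −3 g/dL would be needed to cross −1 at the planning SD. The number of such breaches is unknown and is probably small. This is a cheap improvement to a supporting analysis and does not threaten the trial's conclusion.

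**What to change.** Amend SAP 4.1.2 before database closure:

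- Extend item 6 to hemoglobinopathy, overt GI bleeding, active malignancy, uncontrolled or symptomatic inflammatory disease, peritonitis, severe hyperparathyroidism or marrow fibrosis, and positive anti-EPO antibody or antibody-mediated PRCA. State that the list is exhaustive.
- Add the PD and HD adequacy criteria to item 5.
- Judge both on status at entry, including results on entry status that become known after dosing, such as the Week 1 pre-dose antibody test.

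Do not add departure from Table 3 as an exclusion. At most, list doses that depart from it at Weeks 5 to 17 beside the dose-change tables of SAP 4.3.2.2, once the passages named above have been reconciled.

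The cost is SAP wording and a slightly smaller per-protocol set. No new data are needed. PTH is not among the study laboratory tests in Protocol 4.5.6.1, so that item rests on the site's eligibility record.

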#### **4.3.1 Primary Efficacy Endpoint**

Hb concentration values (g/dL) over time and change in Hb from baseline to evaluation period will be presented in summary tables and graphically. The estimates will be summarized descriptively using means, standard deviation and percentiles.

The individual change from baseline will be reported using summary statistics (including mean, standard deviation and 90% CI of mean change). No formal statistical testing will be performed. Additional analysis will be performed by age category (<5, 5-11, ≥12 years), dialysis type (not yet on dialysis, PD, HD) and previous ESA (epoetin [epoetin alfa or epoetin beta or biosimilar] or darbepoetin alfa), if numbers allow.

The 90% confidence interval (CI) for the average per-patient Hb change from baseline to the evaluation period (weeks 17-21) will be calculated. If the lower limit of the CI is ≥-1 g/dL, the upper limit ≤1 g/dL and the number of dose increases and decreases are approximately balanced across the patients the conversion factor from prior ESA treatment for the first Mircera dose will be considered appropriate.

The Hb change from baseline is calculated on a per-patient basis, using an Area Under the Curve (AUC) approach to calculate an individual's average for both the baseline and evaluation periods and taking the difference. This per-patient change is then averaged over all patients and the confidence interval calculated.

The baseline period is defined as all assessments between the day of first study dose and the previous 35 days. If during the baseline period Hb measurements  $H_0, \dots, H_n$  are taken at timepoints  $t_0, \dots, t_n$ , a time adjusted average baseline Hb value will be calculated by

$$y = \frac{1}{2(t_n - t_0)} \sum_i (H_i + H_{i-1})(t_i - t_{i-1})$$

The value on the day of the first dose is included in the baseline calculation, as this assessment will be performed before the first dose is given.

The average Hb value for each individual during the evaluation period will be calculated using the same method as for the baseline period. The evaluation period is defined as all assessments between Visit 8 (Week 17) and Visit 10 (Week 21) inclusive. Subtracting the baseline period value from the evaluation period value gives the change in Hb concentration (g/dL) between the baseline and evaluation period.

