##### **4.3.2.2 Change in Mircera dose over time**

The change in Mircera dose over time, including the change between the starting dose and the evaluation period, will be analyzed descriptively, overall and by age-group. The ratio of starting dose (Week 1) to the dose at the evaluation period (Week 17) will be summarized by using mean, median, minimum and maximum.

A dose change is defined as a change in the administered dose strength compared to the preceding dose. The number of patients with dose increases, dose decreases and both increases and decreases will be tabulated.

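### The dose-adjustment table pushes dose changes toward decreases for reasons unrelated to the conversion factor, yet the SAP judges the factor on whether increases and decreases balance

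*Protocol*

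**What the plan says.** Protocol 4.3.2.1.1 has the dose adjusted to keep each patient "within a target range of ± 1 g/dL of his or her baseline Hb and between 10.0–12.0 g/dL". The rules are in Table 3.

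- **Relative to baseline**, the triggers mirror each other: a fall of more than 1.0 g/dL prompts an increase, and the reverse ("Hb increases by more than 1.0 g/dL compared with the baseline Hb") prompts a decrease.
- **On the low side**, the absolute triggers begin only once "Hb is less than 10 g/dL and greater than or equal to 9 g/dL", with a further row below 9. Nothing covers a falling Hb near 10, and an Hb of exactly 10.0 triggers nothing by itself.
- **On the high side**, a decrease applies when "Hb is increasing and is approaching 12 g/dL or Hb is greater than or equal to 12 g/dL". There is also a hold rule ("Stop doses until Hb is less than 12.0 g/dL") with no low-side equivalent.
- **Frequency of adjustments**: "They should not be performed more often than once every 4 weeks". In the core study this leaves four decisions after the first dose, at Weeks 5, 9, 13 and 17.

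SAP 4.3.1 calls the conversion factor appropriate if the 90% CI for mean Hb change lies within ±1 g/dL and the "number of dose increases and decreases are approximately balanced across the patients". SAP 4.3.2.2 defines a dose change as any change in administered strength from the preceding dose and adds: "The number of patients with dose increases, dose decreases and both increases and decreases will be tabulated". Neither section gives a margin for balance.

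**The concern.** The balance condition is useful only if a correct conversion factor produces about as many increases as decreases. Table 3 does not guarantee that. Some decreases are prompted while Hb is in target, whereas a patient in target never qualifies for an increase. For example, a patient with baseline 11.8 whose Hb moves from 11.7 to 11.8 is at baseline and in target, yet could be read as rising and approaching 12.

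The size of the push depends on how each site reads *approaching*. Protocol 9.4 plans about 35 sites for about 40 patients, so the reading may differ almost from patient to patient.

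This matters because the balance condition is the part of the decision more specific to the starting dose. Hb at Weeks 17–21 already reflects titration at Weeks 5, 9 and 13, which can mask a poor starting dose in the CI condition. A skewed count could make a correct factor look too high, or make a low one look balanced.

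**Working it through.** **The plan's own figure.** The stated power of about 90% (Protocol 6.1, SAP 2.3) uses n = 26, SD 1.5, true change 0 and a 90% CI within ±1 g/dL.

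- Standard error = 1.5/√26 = 0.294, and 1/0.294 = 3.40.
- Normal approximation: 2Φ(3.40 − 1.645) − 1 = 92.1%.
- With the t critical value on 25 df (1.708): 2Φ(3.40 − 1.708) − 1 = 90.9%.

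The figure is reproduced, but it covers the CI condition only. The documents give no corresponding figure for balance.

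**Simulation of Table 3 under a perfect factor.**

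Inputs from the documents:
- the Table 3 triggers;
- four decisions per patient;
- baseline as the mean of Visits 1 and 2, restricted to 10.0–12.0;
- 28 patients (40 × 0.70).

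Assumptions, not in the documents:
- true baselines uniform on 10–12 or normal with SD 0.5;
- within-patient Hb SD 0.5 or 0.8;
- lag correlation 0.5;
- Hb rounded to 0.1;
- *approaching* means at least 11.8 or 11.5 and above the previous dosing-day value;
- each dose change shifts later Hb by 0 or 0.4 g/dL;
- the hold rule is left out.

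Expected changes per patient, normal baselines, zero shift (ratios taken before rounding):

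| Baseline mean | SD | Rule | Increases | Decreases | Ratio |
|---|---|---|---|---|---|
| 11 | 0.5 | symmetric, out of target only | 0.33 | 0.33 | 1.01 |
| 11 | 0.5 | Table 3, 11.8 | 0.33 | 0.51 | 1.57 |
| 11 | 0.5 | Table 3, 11.5 | 0.33 | 0.77 | 2.38 |
| 11 | 0.8 | Table 3, 11.8 | 0.72 | 0.88 | 1.22 |
| 11 | 0.8 | Table 3, 11.5 | 0.72 | 1.08 | 1.50 |
| 10.7 | 0.5 | symmetric, out of target only | 0.50 | 0.22 | 0.43 |
| 10.7 | 0.5 | Table 3, 11.8 | 0.50 | 0.32 | 0.64 |
| 10.7 | 0.5 | Table 3, 11.5 | 0.50 | 0.51 | 1.01 |

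In 28 patients, the SD 0.8 rows at mean 11 give 28 × 0.72 = 20.2 increases against 28 × 0.88 = 24.6 or 28 × 1.08 = 30.2 decreases.

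**Ranges.** A separately programmed run over both baseline shapes centred on 11, SD 0.5–0.8 and both shifts gave 1.17–1.56 (11.8) and 1.37–2.33 (11.5). The table's 1.57 and 2.38 are the upper ends from the other program. Raising the SD to 1.06 brings the lower ends to 1.12 and 1.25. The boundary at 12.0 without the *approaching* clause gives only 1.06–1.22, so that clause is the main driver. At baseline mean 10.7 Table 3 gives 0.64–1.07, against 0.43–0.71 for symmetric triggers.

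**Chance in one trial.** With baselines centred on 11 and SD 0.5–1.06, decreases exceed twice the increases in 3–34% of 28-patient trials (11.8) or 5–62% (11.5), against 2–15% under symmetric triggers.

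**Testing a replacement measure.** Counting symmetric out-of-target triggers over all visits is itself biased: with baselines centred on 11 and a 0.4 g/dL shift the ratio is 0.67–0.92, because in-target decreases lower later Hb. The same triggers at Week 5 alone, before any dose change, give 0.98–1.01.

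**The case against.** The best defence is that a trigger acting before the upper limit is a reasonable way of staying under it. Protocol 4.3.2.1.1 says some rules are there for safety, and the amendment deliberately clarified Table 3. That stands: only an Hb of exactly 12.0 is a literal overlap between target and trigger. A reader might infer that the table contradicts the target outright, but the documents do not support so strong a reading. The point here is what the asymmetry does to the SAP's count.

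A reader might also infer that a correct factor will be rejected. The documents do not support that either, for three reasons:

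- They give the eligible baseline range but not the distribution within it. At a mean of 10.7 the asymmetry moves the count nearer to balance.
- Balance has no threshold, so no ratio can be said to fail. On an illustrative band in which decreases make up 40–60% of changes, even symmetric triggers with baselines centred on 11 miss by chance in 20–54% of 28-patient trials.
- The counting unit is open. SAP 4.3.1 refers to changes, SAP 4.3.2.2 tabulates patients, and the simulation counts changes.

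The SAP also summarises the ratio of starting dose to Week 17 dose, and the internal monitoring committee recommended continuing unchanged after 12 completers. These give context, but neither defines balance nor separates changes by trigger. The study is exploratory and the CI calculation is unaffected, which limits the weight of the point.

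**Conclusion.** The concern holds in a conditional form. Table 3 adds decreases that do not reflect the conversion factor, and the SAP counts them in judging that factor. With baselines centred on 11, a perfect factor gives an expected decrease:increase ratio of about 1.2–1.6 or 1.4–2.3, depending on whether *approaching* starts at 11.8 or 11.5. With a baseline mean of 10.7 the ratio is about 0.6–1.1, so apparent balance can arise for the wrong reason.

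These sizes rest on the assumed SD (0.5–0.8), lag correlation (0.5) and shift per change (0–0.4 g/dL). The omitted hold rule would probably add to the downward push. Whether the criterion would be met or missed is not determinable from the documents.

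**What to change.** In the SAP, before database lock:

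1. Tabulate increases and decreases by Table 3 trigger, derived from recorded dosing-day Hb and dose and using the dosing baseline of Protocol 4.3.2.1.1 (mean of Visits 1 and 2). Show decreases made while Hb was in target on a separate line. Do the same for held doses, which the strength-change definition does not clearly cover.
2. Judge balance mainly on symmetric out-of-target triggers at Week 5: Hb below 10.0 or more than 1.0 below baseline, against Hb above 12.0 or more than 1.0 above baseline. Show the raw all-visit counts as supportive. Do not apply the symmetric triggers over all visits, because in-target decreases bias that count toward increases.
3. State the counting unit and margin, and read the result against the observed baseline Hb distribution. Even symmetric triggers are unbalanced when baselines are not centred on 11.

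In the protocol, the sponsor must reconcile the row on approaching or reaching 12 with the stated target. No dosing rule is proposed here, and a clarification cannot standardise decisions already made.

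The cost is SAP wording and a derived variable from data already collected. The Week 5 comparison no longer equals the raw count and rests on few events. Taking a quarter of the four-visit symmetric rate, 28 × 0.33/4 = 2.3 to 28 × 0.72/4 = 5.0 patients are expected on each side for SD 0.5 to 0.8. It also reflects only one Mircera dose. The margin should allow for this imprecision.
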